3.3 ENDPOINTS

Primary endpoint of the phase III trial is locoregional recurrence rate 3 years postoperatively. Secondary endpoints are disease free and overall survival at three, five and seven years, rate of distant metastases, port-site and wound-site recurrences, macroscopic evaluation of the resected specimen, 8-week mortality and morbidity, quality of life and costs.

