6.2 SECONDARY ENDPOINTS

6.2.1 *Clinical*

- survival free of cancer recurrence at three, five and seven years
- overall survival at three, five and seven years
- distance of the tumor to the endopelvic fascia and the distal resection margin
- port-site and wound-site recurrences
- distant metastases rate
- 8-week or in-hospital operative mortality and morbidity
- macroscopic evaluation of the resected specimen

6.2.2 *Quality of life*

- duration of in-hospital stay postoperatively
- duration of absence of work
- postoperative health related quality of life (quality adjusted life years), including standardized questionnaires on sexual and bladder function

6.2.3 *Costs (national)*

- in hospital direct and indirect costs
- out-of-hospital postoperative costs

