15.2 FOLLOW-UP FORMS

The follow-up part of the case record forms contains one normal follow-up form to complete each year. Minor complaints or complications can be noted in these forms. Complaints that are more serious or complications necessitating hospital intake, but not related to cancer should be noted in the form for events not related to cancer. In case of recurrences, the recurrence form and the recurrence follow-up form should be completed.

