17.4 DATA COLLECTED DURING POST-OPERATIVE PERIOD

The post-operative period is defined as the period starting when the patient is leaving the operating theatre and ending 8 weeks after that. The day of operation is day 0.

- post-operative day with fluid intake > 1000 ml resumed
- post-operative day with passage of first stool
- day of discharge from hospital
- complications including death and cause of death and number of re-interventions and reasons of further abdominal surgery
- reason and duration of possible readmission in hospital within 8 weeks after surgery
- analgesic requirement during the first three days

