| 1 | Roticulator |  | blue |  | green | firings |
| 2 | Curvature |  | blue |  | green | firings |
| 3 | Linear stapler |  | blue |  | green | firings |
| 4 | Other |  | blue |  | green | firings |

32. blood loss : ml

33. skin to skin time : minutes

COLOR II

Dept. of Surgery, QEII Health Sciences Centre
 [name]
 [name], Halifax, Nova Scotia
 Canada [name]
 [contact]
 [contact]

Date:**Procedure:** LAP / OPEN**Rand nr:****Doctor:**

34. complication(s) : 0 none
 1 bleeding
 2 fixation of the tumor
 3 gastrointestinal perforation
 4 adhesions
 5 hypercapnia
 6 anastomosis related problems
 7 injury to ureter
 8 nerve injury
 9 perforation tumor
 10 other:

35. wound protection : 0 no
 (if yes, please mention kind of) 1 yes please specify:

PLEASE FILL OUT NEXT QUESTIONS IN CASE OF A LAPAROSCOPIC PROCEDURE

36. laparoscopic operative steps : 1 inspection
 2 mobilization of bowel
 3 ligation of main vessels
 4 oral transection of bowel
 5 aboral transection of bowel
 6 resection of bowel
 7 anastomosis

38. conversion : 0 no
 1 yes

39. if appropriate, reason for conversion :

COLOR II

Dept. of Surgery, QEII Health Sciences Centre
[name]
[name], Halifax, Nova Scotia
Canada [name]
[contact]
[contact]

Date:**Procedure:** LAP / OPEN**Rand nr:****Doctor:**

POSTOPERATIVE PERIOD 1-28 days after surgery; day of operation = day 0 (no 40 - 47)**If appropriate, please encircle correct figure, more than one can be encircled per question**

40. date of fluid intake > 1000 ml : (dd-mm-yyyy)

41. date of first passage of stool : (dd-mm-yyyy)

42. date of discharge from hospital : (dd-mm-yyyy)

43. if appropriate, date and nature of complication(s)

date (dd-mm-yyyy):

- 1 anastomotic leakage
- 2 cardiac complications:
- 3 respiratory complications:
- 4 abscess
- 5 ileus
- 6 other:

44. if appropriate, date and nature of re-intervention(s):

date (dd-mm-yyyy):

nature:

45. if appropriate, date and cause of death:

date (dd-mm-yyyy):

cause:

46. if appropriate, date, cause and duration of readmission:

date (dd-mm-yyyy):

cause:

readmission:

COLOR II

Dept. of Surgery, QEII Health Sciences Centre
[name]
[name], Halifax, Nova Scotia
Canada [name]
[contact]
[contact]

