- 64. postoperative adjuvant therapy : 0 no
1 yes
- 65. re-admissions : 0 no
(if yes, please fill out event form) 1 yes
- 66. re-interventions : 0 no
(if yes please fill out event form) 1 yes

COLOR II

Dept. of Surgery, QEII Health Sciences Centre
[name]
[name], Halifax, Nova Scotia
Canada [name]
[contact]
[contact]

Date:**Procedure:** LAP / OPEN**Rand nr:****Doctor:**

RECURRENCE FORM

If appropriate, please encircle correct figure, more than one can be encircled per question

107. date of diagnosis of (re)recurrence (dd-mm-yyyy) :
108. number of recurrence (first, second, etc.) :
109. nature of recurrence : 1 locoregional
2 liver metastasis
3 lung metastasis
4 trocar wound recurrence
5 minilaparotomy wound recurrence
6 laparotomy wound recurrence
7 other :
110. date of cancer related death (dd-mm-yyyy) :

**When completed, please fax this form to the coordinating center:
Dalhousie University, Halifax, Canada**

[contact]

COLOR II

Dept. of Surgery, QEII Health Sciences Centre
[name]
[name], Halifax, Nova Scotia
Canada [name]
[contact]
[contact]

Date:**Procedure:** LAP / OPEN**Rand nr:****Doctor:**

RECURRENCE FOLLOW UP FORM**In case of re-recurrence, please fill out a new recurrence form**111. treatment : *(if appropriate, please describe type of procedure)*

0 no

1 curative resection :

2 palliative resection :

3 other :

112. date of cancer related death (dd/mm/yyyy) :

**When completed, please fax this form to the coordinating center:
Dalhousie University, Halifax, Canada**

[contact]

COLOR II

Dept. of Surgery, QEII Health Sciences Centre
[name]
[name], Halifax, Nova Scotia
Canada [name]
[contact]
[contact]

Date:**Procedure:** LAP / OPEN**Rand nr:****Doctor:**

FORM FOR EVENTS**Please don't forget to mention randomization number in upper right corner**

113. Date of event (dd-mm-yyyy) :
114. Sort event :
115. Date of death (dd-mm-yyyy) :
116. Cause of death :
117. Cause of bowel obstruction : 0 no bowel obstruction
1 herniation
2 strangulation
3 non malignant stenosis
4 other
118. Other complication(s) : 0 no
1 incisional hernia
2 complaints of bowel function (other than ileus)
3 other:
119. Date of re-operation (dd-mm-yyyy) :
120. Nature of re-operation :

**When completed, please fax this form to the coordinating center:
Dalhousie University, Halifax, Canada**

[contact]

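### The postoperative page of the case record form is headed days 1-28, half of the 8-week period that section 17.4 and the secondary endpoint require, so 8-week morbidity would be incompletely ascertained

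*Protocol*

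**What the plan says.** Section 17.4 of the protocol fixes the period: "The post-operative period is defined as the period starting when the patient is leaving the operating theatre and ending 8 weeks after that". It numbers the day of operation as day 0. Among the data for this period it lists complications, death with its cause, re-interventions, and "reason and duration of possible readmission in hospital within 8 weeks after surgery".

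The endpoint follows the same window. The summary in section 3.3 names "8-week mortality and morbidity, quality of life and costs". Section 6.2.1 lists "8-week or in-hospital operative mortality and morbidity". Section 19.1 plans chi-square comparisons of 8-week operative mortality and of complication rates.

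The case record form in Appendix VII collects these data at items 43 (complications), 44 (re-interventions), 45 (death) and 46 (readmission). The page is headed "POSTOPERATIVE PERIOD 1-28 days after surgery; day of operation = day 0".

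Two other forms can receive later events. Section 15.2 sends serious complaints, and complications that lead to admission, to the event form (items 113-120). Minor ones may go on the yearly follow-up form.

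**The concern.** The protocol and its own form define one period, under one name and with one day-0 convention, in two ways. If the form is completed as printed, its only page with codes for leak, cardiac and respiratory complications, abscess and ileus closes at day 28. Anything later depends on forms designed for other purposes.

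At stake is the short-term safety comparison between laparoscopic and open surgery. Complications first appearing after day 28 would be recorded less completely and in different categories from earlier ones. An analysis plan cannot restore an event, a code or a date that no form collected.

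**Working it through.** **Window.** Section 17.4: 8 weeks x 7 = 56 days after the operation. Page heading: days 1 to 28 = 28 days. Gap: 56 - 28 = 28 days (days 29-56), and 28/56 = 50% of the window. This is a share of time, not of events.

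**What each form can supply.** All item numbers are from Appendix VII.

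| Event | Days 1-28 | Days 29-56 |
|---|---|---|
| Death | Item 45, date and cause | Event form items 115-116, date and cause; also the two-week fax report (15.1) and the yearly data (17.6) |
| Re-operation | Item 44, date and nature | Follow-up item 66 triggers the event form; items 119-120 give date and nature |
| Readmission | Item 46, date, cause and duration | Follow-up item 65 triggers the event form; item 113 gives a date; no field for duration |
| Serious or admission-requiring complication | Item 43, dated and coded | Event form items 113-114, dated, with type of event as free text; no codes for leak, abscess, cardiac or respiratory complications |
| Milder complication | Item 43, dated and coded | Yearly form item 63, first due at year 1, no onset date |

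**Reading across the rows.**
1. Death and re-operation keep a date, so both can be placed within 8 weeks.
2. Serious complications can be dated, provided that an event form is completed. Their category must then be rebuilt from free text.
3. Readmission can be dated, but the duration that section 17.4 asks for has no field.
4. A milder complication on day 40 cannot be told from one in month 9, because both would be undated entries on the year-1 form.

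**Size of the loss.** Let f be the share of 8-week complications arising in days 29-56, and c the share of those that reach a dated form. The fraction counted is 1 - f(1 - c). There is no loss if c = 1, and the whole of f is lost if c = 0. If f and c are equal in the two arms, both rates, and so their difference, shrink by this same factor. The protocol gives neither f nor c, so no figure can be put on the loss.

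**The case against.** The strongest reply is that the heading belongs to one page only. The event form has no time window; it asks for "Date of event (dd-mm-yyyy", date and cause of death, and date and nature of re-operation. The yearly form requires an event form whenever it records a readmission or re-intervention. Deaths have further routes. In section 19.1 the 8-week qualifier is attached to mortality, and complication rates carry no clear window. All of this stands, and it limits the point to part of morbidity.

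It does not remove the conflict. Sections 3.3 and 17.4 apply 8 weeks to morbidity and to complications, whatever section 19.1 leaves open. The in-hospital alternative in section 6.2.1 does not help either, because those two sections do not offer it, and a patient still in hospital after day 28 would also fall outside the heading.

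Several stronger readings are tempting, and the documents do not support them:
- **That the case record form stops at day 28 and 8-week morbidity cannot be computed.** The event form contradicts the first part, and its dated fields allow serious morbidity to be derived.
- **That re-interventions after day 28 are lost.** Items 66, 119 and 120 give them a route.
- **That some sites would report 28-day and others 8-week rates.** One form is printed for all centers, and nothing shows that practice would differ.
- **That events on the day of surgery are excluded.** Section 17.4 uses the same day numbering, and items 43-46 take calendar dates.
- **That the comparison is biased toward one arm.** Both arms use the same forms, and the documents give no reason for a difference in capture.

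**Conclusion.** The point holds as an internal inconsistency that affects one secondary endpoint. The postoperative page covers 28 of the 56 days in section 17.4. In days 29-56, milder complications have no onset date. Serious ones depend on an event-triggered form without the item 43 codes, and duration of readmission is not collected. 8-week morbidity would be incompletely ascertained, with a change of instrument at day 28.

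8-week mortality, the primary endpoint and the sample size of 1275 are not affected. The conclusion assumes that the page is completed as its heading says and that event forms are used as section 15.2 describes. The number of complications missed is unknown, and the 50% must not be read as half of them.

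**What to change.** Reconcile the heading of items 40-47 with section 17.4, so that the page covers the period from leaving theatre to 8 weeks, and have it completed at or after 8 weeks. Repeat the date line of item 43 for each complication, since one line is now printed for six codes. With a date per complication, a 28-day rate can still be derived.

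The cost is a new heading, a changed item 43, and completion of the page about four weeks later than now. No change to the sample size or to the planned tests is needed.

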12.2 CONVERSION

Conversion is defined as a change in operative approach to achieve the final goal and will be at the discretion of the individual surgeon for concerns of patient safety, technical difficulties, inability to complete the planned operation for sphincter sparing or associated conditions requiring treatment. Utilizing the extraction site for transverse stapler insertion to accomplish the distal anastomosis will not be considered a conversion. Identification of any grossly visible positive margins or extension into adjacent organs will mandate conversion to an open procedure. Completion of the pelvic dissection through open surgery will be considered conversion. Conversion is defined as a fascial incision longer than 10 cm, utilized to achieve anything other than specimen extraction. (Largest handport size is 8 cm)

13 HISTOPATHOLOGY.

All resected specimens are analyzed by the pathologist. Macroscopical assessment of the quality of mesorectal dissection will be scored in 3 grades.

- Complete: intact mesorectum with only minor irregularities of the mesorectal surface. No defect is deeper than 5 mm. No coning towards the distal margin of the specimen. Smooth circumferential resection margin on slicing.
- Partial incomplete: the majority of the mesorectum has been removed. Moderate coning of the specimen towards the distal margin. At no site is the muscularis propria visible with the exception of the area of the insertion of the levator muscles. Moderate irregularity of the circumferential resection margin.
- Incomplete: mesorectum with defects down onto muscularis propria and/or very irregular circumferential resection margin, coning.

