Date:**Procedure:** LAP / OPEN**Rand nr:****Doctor:**

47. pain medication during first 3 days

Please mention what kind of medication, quantity (mg) and, where appropriate, speed of pump (mg/ml per hour)

Postoperative day 1

1 opiates :

2 non-opiates :

3 epidural :

Postoperative day 2

1 opiates :

2 non-opiates :

3 epidural :

Postoperative day 3

1 opiates :

2 non-opiates :

3 epidural :

COLOR II

Dept. of Surgery, QEII Health Sciences Centre
[name]
[name], Halifax, Nova Scotia
Canada [name]
[contact]
[contact]

Date:**Procedure:** LAP / OPEN**Rand nr:****Doctor:**

Please add this information form for the pathologist to the resected specimen

COLOR II TRIAL

A randomized clinical trial comparing laparoscopic and open surgery for rectal cancer

Dear colleague,

The COLOR II trial is a randomized clinical trial comparing laparoscopic and open surgery for rectal cancer. The primary endpoint is locoregional recurrence three years post-operatively. In order to assess relevant oncological parameters, the pathological examination of the specimen is of utmost importance. Below you'll find the items which will be recorded for the COLOR II trial. You are kindly asked to document these items in your examination report.

Please provide the following data on pathology

- Completeness of resection

Complete	Intact mesorectum with only minor irregularities of the mesorectal surface up to the dissection level. No defect is deeper than 5 mm. No coning towards the distal margin of the specimen. Smooth circumferential resection margin.
Nearly Complete	Moderate bulk to the mesorectum, no visible muscularis propria, moderate coning, irregular circumferential resection margin.
Incomplete	Little bulk to the mesorectum with defects down onto muscularis propria and/or very irregular circumferential resection margin, coning.

- Size of tumor
- Distance of tumor from circumferential resection margin
- Distance of tumor from proximal resection margin
- Distance of tumor from distal resection margin
- If appropriate, position of tumor with respect to peritoneal deflection
- Type and differentiation of tumor
- Tumor tissue in surgical margins (i.e. radicality)
- Number of lymph nodes harvested
- Number of lymph nodes in proximal part of mesentery, that means all lymph nodes not along resected bowel (if none, please mention)
- If appropriate, nature of metastases
- If appropriate, synchronous colorectal pathology

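### The form that travels with the specimen carries a laparoscopic/open field, so the pathologist can see the arm when grading the mesorectum

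*Protocol*

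**What the plan says.** Appendix VII of the protocol contains an information form for the pathologist. The site is told: "Please add this information form for the pathologist to the resected specimen". The header on that page has fields for the date, the procedure ("Procedure: LAP / OPEN"), the randomization number and the doctor. The text below it tells the pathologist that "The COLOR II trial is a randomized clinical trial comparing laparoscopic and open surgery for rectal cancer". It then asks for the completeness of resection in three grades, the distances to the circumferential, proximal and distal margins, and any tumor in the margins. These items are to be documented in the pathologist's own examination report.

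Section 13 states that "All resected specimens are analyzed by the pathologist" and that "Macroscopical assessment of the quality of mesorectal dissection will be scored in 3 grades". Section 6.2.1 lists "macroscopic evaluation of the resected specimen" as a secondary endpoint, and also "distance of the tumor to the endopelvic fascia and the distal resection margin".

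The protocol does not mask the pathologist, and it provides for no central review or second reading. Section 20.3 adds only that specimens are examined under the protocol's own rules.

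**The concern.** Surgeon and patient cannot be blinded to the approach. The person who grades the specimen largely can be, and here the trial's own paperwork works against it: one sheet carries the arm field, names the comparison and requests the graded outcome.

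The grade matters because section 4.4 says that outcome after rectal resection depends mainly on the extent of resection by TME principles, and it cites pathological extent as existing support for the laparoscopic approach. The grade definitions rest partly on degree words (minor or moderate irregularity, moderate coning). Expectations about a new technique could move borderline specimens in one arm, creating a difference or hiding one. Unless specimens are photographed or graded a second time, which the protocol does not require, the analysis could not remove such a shift.

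**Working it through.** **1. What the pathologist can see, and what is read**

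| Item | Place in protocol | Exposure to knowledge of the arm |
|---|---|---|
| Mesorectal grade | 13; 6.2.1; information form | Greatest: partly a judgement, although anchored by the 5 mm defect limit and by visible muscularis propria |
| Choice of blocks for the margin | 13 (one to six blocks, suspicious areas sampled) | Some: sampling is discretionary |
| Circumferential distance | 13 (microscope, Vernier scale); 13.3 (2 mm cut-off, two-digit reporting) | Small: a measurement on the stained slide |
| 3-year locoregional recurrence (primary) | 6.1; 16.2 | None by this route: not read from the specimen |

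**2. The plan's own figure**

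Inputs from 19.1: 10% recurrence in each arm, 5-point margin, two-sided 95% limits, 80% power, 2:1 allocation.

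n(open) = (1.960 + 0.842)² × (0.09 + 0.09/2) / 0.05² ≈ 424, so 848 laparoscopic and 1272 in total. The plan's 425 + 850 = 1275 reproduces, and this point does not change it. The 850 and 425 are used below.

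**3. How large a re-grading would matter (sensitivity only)**

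The protocol gives no rate of complete specimens, so 80%, 85% and 90% are assumptions. It also names no test for the grade: 19.1 lists chi-square for mortality, resection margins and complications. An ordinary two-sided 5% comparison of the proportion graded complete is assumed, with no true difference.

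With the variance held at the unshifted rate p, the smallest significant difference is 1.96 × √[p(1−p)(1/850 + 1/425)], where √(1/850 + 1/425) = 0.0594:

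- p = 0.80: 1.96 × 0.400 × 0.0594 = 4.66 points
- p = 0.85: 1.96 × 0.357 × 0.0594 = 4.16 points
- p = 0.90: 1.96 × 0.300 × 0.0594 = 3.49 points

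A chi-square test pools the two observed rates, so the threshold depends on which arm moves and in which direction:

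| Assumed complete rate | Threshold, pooled variance |
|---|---|
| 80% | 4.4 to 4.9 points |
| 85% | 3.8 to 4.5 points |
| 90% | 3.1 to 3.9 points |

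At 85%, a 5-point shift gives:

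- laparoscopic arm down: pooled rate 0.817, z = 0.05/0.0230 = 2.18, p = 0.030
- open arm down: p = 0.024
- open arm up: p = 0.013
- laparoscopic arm up: pooled rate 0.883, z = 0.05/0.0191 = 2.62, p = 0.009

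**4. The chance of a false signal**

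The thresholds in step 3 are observed differences. If the adverse reading rate is truly 10% or 20% in both arms, and readings in the laparoscopic arm are shifted upwards on average, a significant result in that direction occurs with probability:

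| Average shift | 10% adverse | 20% adverse |
|---|---|---|
| 2 points | 18% | 13% |
| 3 points | 34% | 23% |
| 5 points | 71% | 51% |

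Without a shift it is 2.5%. None of this estimates the bias that disclosure would cause; the documents contain nothing from which to estimate it.

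**The case against.** The protocol never promises blinded pathology, so nothing is contradicted. The same header stands on every case record form page and is probably a template. What is printed is an unfilled option, so disclosure is an inference. The grades have firm anchors as well as degree words. Section 13.4 calls for close cooperation between surgeon and pathologist for the R classification, so complete masking is unrealistic. The sensitivity figures show what difference would be significant, not that disclosure produces it.

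Most of this stands, and it limits the point. It does not remove it: a field on a form that must accompany the specimen will ordinarily be filled in, and no instruction says otherwise.

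A reader might infer more than the documents support:

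- *That the margin reading is compromised as much as the grade.* The circumferential distance is measured on the stained slide, and a slide can in principle be re-read. Only block selection leaves real room. The distance to the endopelvic fascia is also estimated by the radiologist before surgery (11.1), so it is not clearly a specimen reading.
- *That the pathology page (items 48-60) also discloses the arm to the pathologist.* It has the same header, but the information form asks for the items in the examination report. Nothing shows who completes the page.
- *That a 5-point shift has one definite p-value.* Holding the variance at the unshifted 85% rate gives 0.018. The pooled test gives 0.009 to 0.030.
- *That masking is free and complete.* The contact in 13.4 and informal routes both limit it.

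**Conclusion.** The point holds as an avoidable weakness in one partly subjective secondary endpoint, with a lesser effect on block selection. The form sent with the specimen can tell the pathologist the arm while asking for the mesorectal grade, and the protocol has no safeguard against this. The primary endpoint and the sample size are untouched.

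The size and direction of any bias are unknown. If 80 to 90% of specimens are graded complete, a difference of roughly 3 to 5 percentage points created by grading alone would reach p<0.05 with 850 and 425 patients. That range rests on the assumed rate and on an assumed two-sided test of the grade. Correcting the form is a cheap improvement, not the repair of an error that invalidates the plan.

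**What to change.** - Delete the procedure field from the information form that goes with the specimen and keep the randomization number. Do the same on the pathology page (items 48-60) if the pathologist completes it. No data are lost, because items 2 and 6 of the identification page already link the randomization number to the randomized procedure.
- Add to section 13 that the form sent with the specimen does not state the surgical approach, and that the pathologist records the mesorectal grade without being told the arm and before any discussion with the surgeon for the R classification (13.4).

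The cost is one or two reprinted form pages and a short addition to section 13, with no extra reader or procedure. The downside is that masking will be imperfect where the approach becomes known by other routes. The change helps only specimens graded after it is made.

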metastases [20, 21]. In a recent review of current literature the incidence of port site metastasis is 1% or less[22]. Experience of the surgeon and standardization of the technique seem to play an important role [23-25].

The pathogenesis of abdominal wall metastases remains unresolved. Inadvertent grasping of the tumor and extraction of the tumor through narrow incisions of the abdominal wall are likely to play an important role. Precise localization of the tumor and protection of either the abdominal wall or the specimen during extraction are therefore used by most experienced surgeons. Whether the increased intra abdominal pressure or the use of CO₂ gas to establish the pneumoperitoneum compromise cancer free survival remains uncertain. Some experimental studies have shown that gasless laparoscopy results in less tumor growth [26].

Laparoscopic surgery appears to be associated with less operative trauma and blood loss than open surgery. These factors are considered beneficial for survival [27, 28]. Experimental studies have shown that tumor take and growth are significantly less after laparoscopic surgery [29, 30]. Clinical studies on interleukin-6 response to open and laparoscopic colectomy showed significant lower levels of interleukin-6 after laparoscopic procedures, indicating a lower degree of surgical trauma and less attenuation of immunity [22, 31].

The motives to approach colorectal disease laparoscopically are similar to those of laparoscopic cholecystectomy. Compared to open cholecystectomy, laparoscopic cholecystectomy is associated postoperatively with less pain, reduced respiratory impairment, earlier return of gastro-intestinal function, earlier mobilization, shorter hospital stay, earlier return to daily activities and work, improved cosmetic results and less incisional hernias [32, 33]. These same advantages are likely to apply to laparoscopic colorectal surgery.

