18.2 COSTS

Direct and indirect medical cost driving medical events will be assessed for the entire trial population based on data from the case record forms from the operation and the follow up period and also based on data from the Quality of Life substudy. The method has been described earlier (ref: Björholt I, Janson M, Jönsson B, Haglund E. Principles for the Design of the Economic Evaluation of COLOR II: an International Clinical trial in Surgery Comparing Laparoscopic and Open surgery in Rectal Cancer. *Int J Technol Assess Health Care* 2006;22(1):130-5.) Thereafter medical costs will be applied on a national basis for national health economy analyses.

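### Length of readmission is asked only on the day 1-28 form, although section 17.4 requires it to 8 weeks and section 18.2 draws costs from the follow-up forms

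*Protocol*

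**What the plan says.** **Endpoint.** Protocol section 6.2.3 lists costs as a secondary endpoint, including "in hospital direct and indirect costs". It gives no time window.

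**Source of cost data.** Section 18.2: "Direct and indirect medical cost driving medical events will be assessed for the entire trial population based on data from the case record forms". The forms meant are those of the operation and the follow-up period. The sentence adds that the assessment is "also based on data from the Quality of Life substudy". It refers to a published design paper for the method, and national costs are applied afterwards.

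**Readmission data required.** Section 17.4 sets the post-operative period at 8 weeks and lists "reason and duration of possible readmission in hospital within 8 weeks after surgery".

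**Readmission data on the forms (Appendix VII).** The early form is headed "POSTOPERATIVE PERIOD 1-28 days after surgery; day of operation = day 0" and contains "46. if appropriate, date, cause and duration of readmission". The next scheduled form is the yearly visit form. Its items 65 and 66 ask yes or no for re-admissions and re-interventions, each with the instruction "if yes, please fill out event form". Section 15.2 likewise sends hospital admissions unrelated to cancer to the event form, and recurrences to the two recurrence forms.

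**The concern.** The protocol asks for a quantity in its text and relies on the follow-up forms for costs, but after day 28 the forms have no field from which that quantity can be obtained. There are two parts:

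- For days 29 to 56, the text and the forms contradict each other. Section 17.4 requires the length of a readmission, and no form headed for that interval asks for it.
- Beyond 8 weeks there is a gap. Section 18.2 includes the follow-up forms as a cost source, but those forms cannot show how long a patient stayed in hospital.

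Hospital days are commonly a large component of in-hospital cost. The matter has to be settled on the forms, because an analysis plan can choose a costing method but cannot supply discharge dates that nobody recorded.

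**Working it through.** The protocol states no figure to reproduce here. The check is a field-by-field comparison, followed by an illustration of scale.

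**Step 1. What each form can give for a readmission**

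| Form | Period | Start of stay | End or length of stay |
|---|---|---|---|
| Postoperative form, item 46 | days 1-28 | yes | yes (duration) |
| Yearly follow-up form, items 61-66 | years 1-7 | no (yes/no only) | no |
| Form for events, items 113-120 | any later event | item 113, a general event date not labelled as admission | no |
| Recurrence form, items 107-110 | at recurrence | date of diagnosis only | no |
| Recurrence follow-up form, items 111-112 | after recurrence | no (type of treatment only) | no |

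The remaining items on the event form are event type in free text (114), date and cause of death (115-116), cause of bowel obstruction (117), other complications (118), and date and nature of re-operation (119-120).

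**Step 2. Text against forms**

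- Section 17.4 requires length of readmission to 8 weeks = 56 days. Item 46 stands under a heading that stops at day 28. The uncovered part is 56 - 28 = 28 days, half of the required period.
- Follow-up lasts 7 years. The share with a field for length of readmission is 28 / (7 x 365.25) = 1.1%. If item 46 were extended to 8 weeks it would be 56 / (7 x 365.25) = 2.2%.

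**Step 3. Whether the second source fills the gap**

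Section 18.2 also names the quality of life substudy. Item 16b records participation as yes or no for each patient, so the substudy need not cover the whole trial. Of the instruments in section 18.1, only the health and care questionnaire suggests by its name that it covers use of care. It is optional, belongs to the Dutch national study, and ends at week 8.

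**Step 4. What is lost and what is kept**

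Let r be the mean number of late readmissions per patient and L the mean stay, with subscripts l (laparoscopic) and o (open). The difference between arms in late hospital days per patient is

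r_l L_l - r_o L_o = (r_l - r_o) x (L_l + L_o)/2 + (L_l - L_o) x (r_l + r_o)/2.

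The first term can be approximated from the forms by counting events and applying a standard stay or unit cost. The second term cannot, because neither L_l nor L_o is collected.

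**Step 5. Scale (assumptions, not trial data)**

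The protocol gives neither a late readmission rate nor a late length of stay. Assume r from 0.05 to 0.20 (at most one readmission per patient) and L from 3 to 10 days, equal in both arms:

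- Lowest: 0.05 x 3 = 0.15 unrecorded days per patient. This is 850 x 0.15 = 127.5 days in the laparoscopic arm and 425 x 0.15 = 63.75 in the open arm.
- Highest: 0.20 x 10 = 2.0 unrecorded days per patient, or 1700 and 850 days.

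By the second term in step 4, each day of difference between arms in mean late stay would then hide 0.05 to 0.20 hospital days per patient. The documents give no basis for assuming that such a difference exists, or in which direction.

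**The case against.** The strongest reply is that section 18.2 speaks of cost-driving events, with national costs applied afterwards. This fits costing per event. The forms capture the events: incisional hernia, bowel obstruction treated operatively or conservatively (item 63a), cause of obstruction, and nature and date of re-operation. The method is deferred to a published paper that is not at hand and may set the time horizon or name other sources. Section 6.2.3 gives no window, so in-hospital costs could mean the index admission, which items 7 and 42 date.

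Much of this stands, and it rules out several stronger readings that a reader might infer:

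- *The event form has no admission date.* Item 113 can serve as one, although it is not labelled so. The end or length of the stay is what is missing.
- *Late admissions cannot be costed.* They can be costed per event. Only the days are lost.
- *The cost comparison is biased.* The documents do not show this. The one late benefit named is "improved cosmetic results and less incisional hernias" in section 4.3, carried over from cholecystectomy as likely to apply. A difference in bowel obstruction is not predicted, and most of the named benefits are early. Fewer hernias would still show in event counts.
- *A large share of hospital days is missing.* Any such figure rests on assumed rates and stays.

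The reply does not remove the contradiction for days 29 to 56. Section 17.4 requires duration there, whatever the costing method. A center might write such a readmission under item 46 despite the heading, but then practice would vary between centers.

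**Conclusion.** The point holds in a limited form. After day 28 the forms do not yield length of stay for a readmission. For days 29 to 56 this contradicts section 17.4. Beyond 8 weeks it leaves section 18.2 with events but no hospital days. A difference between arms in the length of late stays would not appear in the cost endpoint, while a difference in the number of late events would.

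The effect on the cost comparison cannot be sized from the documents, and its direction is unknown. The range of 0.15 to 2.0 unrecorded days per patient only illustrates the stated assumptions. The relevance beyond 8 weeks rests on reading section 18.2 as extending in-hospital costs into follow-up, and the cited method paper could narrow that. The contradiction with section 17.4 needs no such reading. Only a secondary endpoint is touched; the primary endpoint is unaffected. The change is worth making because it is cheap and the missing dates cannot be recovered at the analysis stage.

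**What to change.** 1. Add date of admission and date of discharge (or duration of stay) to the form for events and to the recurrence follow-up form.
2. Add readmission as a coded event type beside the free text of item 114, so that a readmission can be told apart from other events.
3. Reconcile the 28-day heading of the postoperative form with the 8-week period in section 17.4, so that every center records readmissions over the same interval.

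The cost is a few fields on existing forms and a small amount of extra data entry. No visit, examination or questionnaire is added. Collecting the same dates later would mean retrieving hospital records across all centers.
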